13.4 Statistical Analysis Plan

13.4.1 Primary Endpoint

Treatment Efficacy Decision Rules:

13.4.1.1 Interim Analysis

One interim analysis will be performed to assess treatment futility for each arm separately. For each given treatment arm, the R0 resection rate will be evaluated when surgical data become available for first 30 evaluable patients, approximately 8 months after trial activation. If at most 11 patients (i.e. ≤ 11 patients) among 30 evaluable patients underwent R0 resection, then the given treatment arm will be deemed not promising and the accrual to this treatment arm will be terminated. An evaluable patient is defined as any patient who signed informed consent, deemed eligible by central review and received any protocol-defined treatment.

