1.2 Rationale for Trial Design

Herein we propose to evaluate the efficacy of two rational neoadjuvant treatment backbones in a randomized study. The study builds upon our previous work as requested by CTEP and will define standard preoperative treatment regimens to which future novel regimens can and will be compared in subsequent randomized trials.

We have proposed a randomized frequentist design using exact binomial distribution for this study. This design focuses on evaluating whether clinically meaningful improvement of survival rate can be achieved by the tested regimens comparing to historical data. The evaluation of each treatment arm will be conducted separately, based on a practical assessment of whether the arm is “clinically relevant” alone, as well as the outcome comparisons between two treatments if both arms are deemed promising at the end of the trial. This study uses a critically important interim endpoint (R0 resection rate) that is different from the final endpoint (18 month OS rate) and an interim analysis which allows elimination of any futile arm after only 30 patients enrolled to that arm. If both arms are deemed promising at the end of the trial, a pick-a-winner strategy will be employed to choose one arm as the “winner”. Using a fast maturing end point, R0 resection rate, for interim analysis prevent the possibility of halting the trial at interim analysis while the whole study still powered to detect clinical meaningful improvement in OS rate.

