7.0 TREATMENT PLAN/INTERVENTION

NOTE: Arm 2 closed to new patient enrollment on 08/13/2018, and further Arm 2 treatment for enrolled patients ceased as of 08/13/2018.

Protocol treatment is to begin \leq 14 days of registration.

For questions regarding treatment, please see the study contacts page.

It is acceptable for individual chemotherapy doses to be delivered \leq a 24-hour (business day) window before and after the protocol-defined date for Day 1 of a new cycle. For example, if the treatment due date is a Friday, the window for treatment includes the preceding Thursday through the following Monday. In addition, patients are permitted to have a new cycle of chemotherapy delayed up to 7 days for major life events (e.g., serious illness in a family member, major holiday, vacation that cannot be rescheduled) without this being considered a protocol violation. Documentation to justify this delay should be provided.

Surgery and imaging will be conducted at the registering institution. Radiation therapy must be performed at a radiation therapy facility participating in the IROC monitoring program. Chemotherapy may be given at a non-registering institution. All protocol conduct must be followed and the registering institution is responsible for ensuring all data is reported per protocol. Please refer to the Alliance policy and procedures document posted on the Alliance website for the policy on engagement in research by non-registering institutions. If the NCTN Group credited for enrollment is a non-Alliance Group, then other requirements from the credited Group may apply.

Patients will be randomized to either Arm 1 or Arm 2 (closed to new patient enrollment on 08/13/2018) of the study. Patients will progress through treatment in the absence of any criteria described in [Section 12.1.3](#).

Patients on both Arm 1 and Arm 2 will receive 4 cycles of mFOLFIRINOX and then undergo restaging imaging studies, as per [Section 7.4.1](#). These scans are NOT centrally reviewed.

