After the first set of restaging scans, patients who do not show progression on the local read per [Section 12.1.3](#) will be treated as follows: patients on Arm 1 will receive 4 additional cycles of mFOLFIRINOX, and patients on Arm 2 will receive 3 additional cycles of mFOLFIRINOX and then hypofractionated radiotherapy per [Section 7.2](#). These additional cycles of mFOLFIRINOX for both Arm 1 and Arm 2 should start within 14 days after cycle 4 day 1 unless dose modifications indicate delay.

After preoperative therapy is completed, patients will be restaged, and, if still considered a surgical candidate for resection per the criteria of [Section 3.2.1](#) after central review, will proceed to surgery per [Section 7.3](#). Surgery must occur 4 to 8 weeks after last dose chemotherapy (Arm 1) or of radiation (Arm 2).

Patients considered inappropriate for surgery will go off of study treatment, and are to be followed per the follow-up schedule provided in the study calendar ([Section 5.0](#)).

Following surgery, patients will receive post-operative chemotherapy with 4 cycles of FOLFOX starting 4 to 12 weeks from date of surgery.

Treatment will continue until disease progression or unacceptable adverse event or inability to tolerate treatment even with all allowed dose reductions, or completion of the full treatment program and entrance onto clinical follow-up. Also, see Sections [12.1.3](#) and [12.3](#) for additional information regarding discontinuation of treatment.

See [Section 8.1](#) for ancillary/concomitant therapy guidelines.

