13.2 Sample Size

We anticipate enrolling a maximum of 124 evaluable patients (62 per arm) per statistical design. Additional 10 (5 per arm) patients will be accrued to account for cancelations, ineligibilities, major violations, and lost-to-follow up, etc. Thus the total targeted accrual will be 134 patients.

We anticipate to pre-register 5 patients per month. Since we estimate 80% of patients who are pre-registered for central review will be randomized to therapy, the actual accrual will be 4 patients per month. Thus, we expect to pre-register 168 patients to reach the targeted accrual of 134 patients. The accrual period of this study is estimated to be 34 months.

We also expect that 40% of patients randomized to therapy will be off protocol treatment prior to surgery (i.e. will not undergo surgery). Therefore we expect that of the 134 patients, 80 will proceed to surgery. The primary endpoint, overall survival at 18 month post randomization, is well-defined even among patients who do not receive surgery. Therefore, the percentages of patients who do not undergo surgery do not affect the trial design.

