13.4.1.2 Final Analysis

The primary efficacy analysis will be performed on 18-month OS rate for the two treatment arms, separately, based on all evaluable patients. For each given treatment arm, if full accrual is reached and at least 36 patients (i.e. ≥ 36 patients) out of 62 evaluable patients are alive up to 18 months after randomization, the regimen of the evaluated arm will be considered worthy of further testing in this disease population. Otherwise, the regimen will be deemed inefficacious. The final analysis will be carried out approximately 18 months after the last patient, in each arm, is enrolled. This will occur approximately 52 months after trial activation.

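### The per-arm R0 futility look is dated month 8 and placed after only 30 enrolments, but the plan's own accrual and time to surgery put it at about months 19–22 or later, with about 38–44 of 67 per arm enrolled

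*Combined protocol and SAP*

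**What the plan says.** Section 13.4.1.1 plans one futility analysis in each arm separately: "the R0 resection rate will be evaluated when surgical data become available for first 30 evaluable patients, approximately 8 months after trial activation". An arm with 11 or fewer R0 resections among those 30 closes to accrual. Section 1.2 presents this as a feature of the design: "an interim analysis which allows elimination of any futile arm after only 30 patients enrolled to that arm".

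The accrual inputs are in section 13.2. Of 5 pre-registrations per month, 80% are expected to be randomized, so "the actual accrual will be 4 patients per month". The design has 62 evaluable patients per arm, and "Additional 10 (5 per arm) patients will be accrued to account for cancelations" and other losses, which makes 67 per arm and 134 in all. "The accrual period of this study is estimated to be 34 months". Section 13.4.1.2 dates the final analysis 18 months after the last enrolment: "This will occur approximately 52 months after trial activation".

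The path to surgery is in section 7. Treatment starts no later than "14 days of registration". Section 7.1.1 gives 8 cycles of 14 days in Arm 1 and 7 in Arm 2. Sections 7.2.1.2 and 7.2.1.3 have Arm 2 radiation start at least 5 days after the last chemotherapy dose and run over 1–2 weeks. Section 7.0 sets the surgical window: "Surgery must occur 4 to 8 weeks after last dose chemotherapy (Arm 1) or of radiation (Arm 2").

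**The concern.** The look needs surgical results on 30 patients in one arm, so 60 patients across two equal arms. At 4 per month the whole trial has 32 randomized at month 8, and most of those have not reached the end of preoperative treatment. The stated date cannot be met on the stated inputs.

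The claim in section 1.2 is affected in the same way. Patients keep entering while the first 30 go through treatment and surgery, unless accrual is held. Section 13.4.1.1 states no hold. The suspensions in section 13.5 are safety rules, and section 1.2 gives avoiding a halt as the reason for choosing a fast-maturing interim endpoint. At stake is how much protection from a futile regimen the design claims to offer, and when the only planned efficacy-based look can be expected.

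**Working it through.** **The plan's own figures first.** Accrual: 134 / 4 = 33.5 months (stated 34). Final analysis: 34 + 18 = 52 months (stated 52). Pre-registrations: 134 / 0.8 = 167.5 (stated 168). Interim rule, exact binomial: P(X ≤ 11 of 30) = 43.1% at a true R0 rate of 40% and 0.83% at 60% (stated 43% and 0.8%). All of these reproduce, and the first two confirm that 4 per month is a whole-trial rate. The 8-month date does not reproduce. The nearest matches are 30 / 4 = 7.5 months, or 30 × (67/62) / 4 = 8.1 months. Both give one arm the whole-trial rate and allow no time to surgery.

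**Enrolment of 30 per arm.** Rate per arm: 4 / 2 = 2 per month.
- Month 8: 8 × 2 = 16 per arm.
- 30th patient: 30 / 2 = 15.0 months.
- With the sample-size inflation as an approximation to attrition: 30 × 67/62 = 32.4 enrolled; 32.4 / 2 = 16.2 months.

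**Registration to surgery** (months = weeks / 4.348).
- Arm 1, earliest: start at once, cycle 8 dose at week 14, plus 4 weeks = 18 weeks = 4.1 months.
- Arm 1, latest without delays: 2 + 14 + 8 = 24 weeks = 5.5 months, counting from the last dose as section 7.0 does.
- Arm 2, earliest: cycle 7 dose at day 84, plus 5 days, plus 4 days from first to last fraction, plus 28 days = 121 days = 17.3 weeks = 4.0 months.
- Arm 2, latest: 2 + 14 + 2 + 8 = 26 weeks = 6.0 months. This assumes radiation starts after cycle 7 ends; the protocol gives only the minimum gap.

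**Look date and enrolment.** Look = enrolment time + time to surgery. Enrolled per arm = 2 × look. Spared = 67 − enrolled.

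| Arm | Attrition | Look (month) | Enrolled of 67 | Spared by a stop |
|---|---|---|---|---|
| 1 | none | 19.1–20.5 | 38.3–41.0 | 26.0–28.7 |
| 1 | 67/62 | 20.3–21.7 | 40.7–43.5 | 23.5–26.3 |
| 2 | none | 19.0–21.0 | 38.0–42.0 | 25.0–29.0 |
| 2 | 67/62 | 20.2–22.2 | 40.4–44.4 | 22.6–26.6 |

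Stopping at 30 would spare 67 − 30 = 37, or 67 − 32.4 = 34.6 with inflation.

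**What month 8 would require.** By then only 2 × (8 − 6.0) = 4 to 2 × (8 − 4.0) = 8 patients per arm have been in the trial long enough for surgery. Section 13.2 expects 40% never to reach it, so about 0.6 × 4 = 2.4 to 0.6 × 8 = 4.8 would have been operated on. Having 30 per arm at that point needs 60 / (8 − 3.98) = 14.9 to 60 / (8 − 5.98) = 29.7 randomizations per month in total. Even 30 patients pooled over both arms would have surgical data only at 7.5 + 4.0 = 11.5 to 7.5 + 6.0 = 13.5 months.

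**Sensitivity.** A simulation with Poisson accrual of 2 per arm per month, 62/67 evaluable, 40% leaving treatment at a random time before surgery and surgery at 18–26 weeks gives a median look at month 21.0 (interquartile range 19.0–23.0) and a median of 42 enrolled in the arm (40–45). Patients who leave early are known non-R0 sooner, but the last few who reach surgery still set the date.

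**The case against.** The strongest reply is that nothing operational depends on the date. The look is triggered by data on 30 evaluable patients, and month 8 is only an approximate gloss. The DSMB reviews accrual at least twice a year (section 13.5), so it is unlikely to be misled for long. This stands, and it keeps the severity down. It does not make the date right.

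Section 1.2 is background rationale, and its 30 patients can be read as the analysis sample. That is a fair reading of the intent, but the sentence counts patients enrolled, and no section states the 35–37 saving or a smaller one. The 35–37 is what the sentence implies, not a figure from the plan.

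The 67/62 inflation also covers major violations and loss to follow-up, which do not remove a patient from the evaluable set in section 13.4.1.1, so the upper enrolment figures are probably somewhat high. In the other direction, the range leaves out dose delays that sections 7.0 and 8.2 permit, pathology reporting and slow site start-up. Months 19–22 is therefore a forecast without delays, and the firm statement is that the look falls no earlier than about month 19.

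Arm 2 is closed, so a rate of 2 per arm per month no longer describes current accrual. This stands too: any replacement date must be labelled as belonging to the two-arm design.

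**Conclusion.** The date in section 13.4.1.1 and the enrolment count in section 1.2 do not follow from the plan's inputs. The look falls about 11–14 months later than stated, with about 38–44 of 67 per arm (57–66%) enrolled, about 38–43 in Arm 1. A futility stop spares roughly 23–29 enrolments per arm. This rests on equal allocation, steady accrual of 4 per month from activation, no accrual hold and no treatment delays.

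A reader might infer more, and the documents do not support it. The futility rule is not invalid: its trigger and its 43% and 0.8% do not involve calendar time, nor does the 82% power. There is no evidence that a look was taken at month 8 on immature data, or that the closure of Arm 2 rested on one: the documents give no activation date and do not say whether either arm's look had taken place. That the 8 months came from applying the whole-trial rate to one arm is a plausible explanation, not a stated one. The look also keeps its value, since it can still spare about a third or more of an arm (22.6 / 67 = 34% to 29.0 / 67 = 43%). Severity is low to moderate: a stated timeline and design property need correcting, not a decision rule.

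**What to change.** In section 13.4.1.1, delete the 8-month date, or replace it with: *about 19–22 months or later after activation under the original two-arm accrual assumption of 4 per month*.

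In section 1.2, replace the clause about 30 enrolled patients with: *based on surgical data from the first 30 evaluable patients in that arm, by which time about 40 of the planned 67 are expected to be enrolled under the original two-arm accrual assumption*.

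The 30-patient trigger, the 11-of-30 rule, the 43% and 0.8% stopping probabilities, the 82% power and the 34- and 52-month dates stay as they are. No accrual hold is proposed, so the timeline does not lengthen. The cost is two wording edits, a later stated look and a smaller stated saving in patients.

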13.4.1.2 Final Analysis

The primary efficacy analysis will be performed on 18-month OS rate for the two treatment arms, separately, based on all evaluable patients. For each given treatment arm, if full accrual is reached and at least 36 patients (i.e. ≥ 36 patients) out of 62 evaluable patients are alive up to 18 months after randomization, the regimen of the evaluated arm will be considered worthy of further testing in this disease population. Otherwise, the regimen will be deemed inefficacious. The final analysis will be carried out approximately 18 months after the last patient, in each arm, is enrolled. This will occur approximately 52 months after trial activation.

13.4.1.3 Analysis Plan

The treatment arm specific 18 month OS rate and 95% confidence interval will be estimated based on standard method [39]. Chi-squared test (or Fisher's exact test if the data in contingency table is sparse) will be used to compare 18 month OS rates among treatment arms. Overall survival within each arm will be summarized by Kaplan-Meier method. Median, 1-year and 2-year rates will be estimated based on Kaplan-Meier curves.

If both arms are deemed worthy of further testing in this disease population, a log-rank test will be used to compare the median OS between the two arms. A "pick-the-winner" approach will be utilized, meaning that the nominally better arm (the arm with higher 18-month OS rate, by any amount) will be prioritized for future study.

13.4.2 Secondary Endpoints

13.4.2.1 Event-free Survival

The distribution of event-free survival will be estimated using the method of Kaplan-Meier in each arm. Event-free survival will be compared between treatment groups using the log-rank test. The correlation between pCR status and event-free survival time will be assessed by Cox model with landmark approach.

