2.3 Other Objective

Results of the primary analysis will be examined for consistency, while taking into account the stratification factors and/or covariates of baseline overall QOL, mental well-being, physical well-being, and fatigue.

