13.3 Power Justification

The primary aim of this randomized phase II study is to evaluate 18-month OS rate in patients with borderline resectable cancer of the head of the pancreas treated neoadjuvantly using one of the following regimens: 1) Arm 1: 8 cycles of systemic FOLFIRINOX or 2) Arm 2: 7 cycles - of systemic FOLFIRINOX followed by short-course hypofractionated radiation therapy. All patients who are able to undergo subsequent surgery will also receive 4 cycles of postoperative FOLFOX. Eligible patients will be randomized and stratified by ECOG performance score onto two arms. Within each arm, single-arm sequential design with one interim analysis for futility will be implemented. The final efficacy analysis and interim analysis will be based on 18-month OS rate and R0 resection rate, respectively, and evaluated in each arm separately. The comparison of OS between arms will be carried out only if both arms are deemed promising at the end of the trial. “Pick-a-winner” strategy will be implemented to choose one treatment strategy for recommendation.

An extensive literature review was conducted to evaluate median OS and R0 resection rate in patients purported to have “borderline resectable” tumors who received chemo, chemoRT, etc. were conducted. Twenty-six studies published between 2004 and 2015 are identified with number of borderline resectable patients range from 8 to 129. All but three of these studies are retrospective studies.

The following table summarizes the historical data of median OS and R0 resection rate among all patients started treatment, including both patients with and without surgery.

Time era	Among Studies with N > 20				Among Studies with N > 50			
	N of studies	Weighted	Median	Range (IQR)	N of studies	Weighted	Median	Range (IQR)
Median OS in months								
Prior to 2012	6	21.3	21.5	14.2 – 25 (18.0 – 22.8)	3	22.0	22.0	14.2 – 25 (21.5 – 22.5)
2012 and later	9	21.2	19.9	17.2 – 28 (18.0 – 23.6)	6	21.2	21.0	17.2 – 28 (17.9 – 23.2)
All studies	15	21.2	21.0	14.2 – 28 (17.6 – 23.3)	9	21.5	22.0	15 – 28 (19.0 – 23.0)
R0 Resection Rate Among All Patients Started Neoadjuvant Treatment								
Prior to 2012	6	41.4%	36.9%	30 – 59%	3	43.0%	38.8%	30 – 59%
2012 and later	9	61.2%	54.4%	42 – 92%	6	60.0%	54.2%	42 – 92%
All studies	15	53.0%	53.4%	30 – 92%	9	52.8%	53.9%	37 – 92%

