13.4.2.2 R0 Resection Rate

R0 resection rate and confidence intervals for the R0 resection rate will be calculated according to the approach of Duffy and Santner. Chi-square test (or Fisher's exact test if the data in contingency table is sparse) will be used to compare R0 resection rate between treatment arms. Sensitivity analysis will be conducted among patients in cohort 1) and cohort 2). The association between R0 resection rate and OS/PFS will be assessed by log-rank test and Cox model.

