13.4.2.3 Pathologic Complete Response (pCR) Rate

pCR rate and confidence intervals for the pCR rate will be calculated according to the approach of Duffy and Santner. Chi-square test (or Fisher's exact test if the data in contingency table is sparse) will be used to compare pCR resection rate between two treatment arms. Sensitivity analysis will be conducted among patients in cohort 1) and cohort 2). The association between pCR rate and OS/PFS will be assessed by log-rank test and Cox model.

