13.4.2.4 Adverse Events (AE)

For CTCAE data, the frequency tables will be reviewed to determine the patterns. The overall adverse event rates will be compared between treatment groups using Chi-square test (or Fisher's exact test if the data in contingency table is sparse).

PRO-CTCAE data will, at minimum, be analyzed similarly to CTCAE data. Reasons for missed PRO-CTCAE assessments will be collected and we will describe the extent of missing data as well as its patterns and causes. The initial analysis of each PRO-CTCAE item will use all available scores in an analysis which mirrors the approach used for the CTCAE data. Supplemental analysis will use model-based multiple imputation incorporating baseline patient characteristics and physician-rated performance status (which is collected at each cycle). CTCAE data may be incorporated as axillary data into multiple imputation models for AEs which are captured by both PRO-CTCAE and CTCAE. Results from supplemental analysis will be descriptively compared to the results of the initial analysis to assess the robustness of results to missing data. Since a preferred or optimal statistical methodology for PRO-CTCAE data is yet to be determined, additional analyses of PRO-CTCAE data beyond those specified above may be undertaken based on the current state of the science at time of data maturity for this study.

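### Randomization is stratified by ECOG performance status, but the between-arm log-rank tests for EFS and, if triggered, OS are not; the likely loss is small and the remedy is wording only

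*Combined protocol and SAP*

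**What the plan says.** **Assignment.** Section 13.3: "Eligible patients will be randomized and stratified by ECOG performance score onto two arms". Section 4.7 lists ECOG PS, 0 vs 1, as the only stratification factor.

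**Log-rank comparisons.** For EFS, Section 13.4.2.1: "Event-free survival will be compared between treatment groups using the log-rank test". For OS, Section 13.4.1.3, once both arms have been judged worthy of further testing: "a log-rank test will be used to compare the median OS between the two arms". Neither names strata. The EFS test carries no such condition.

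**Binary comparisons.** Chi-square, or Fisher's exact test for sparse tables, serves 18-month OS ("will be used to compare 18 month OS rates among treatment arms", 13.4.1.3), R0 resection ("will be used to compare R0 resection rate between treatment arms", 13.4.2.2), pCR ("will be used to compare pCR resection rate between two treatment arms", 13.4.2.3) and adverse events ("The overall adverse event rates will be compared between treatment groups using Chi-square test", 13.4.2.4). None names strata.

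**The one reference to the factor in analysis.** Section 2.3: "Results of the primary analysis will be examined for consistency, while taking into account the stratification factors and/or covariates". It covers the primary analysis only and gives no method.

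**Status of Arm 2.** Sections 4.7, 7.0 and 13.0 record that Arm 2 closed to new patients on 08/13/2018.

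**The concern.** Randomizing within PS strata balances the arms on PS. This removes from the true variance of the treatment contrast the part that comes from chance PS imbalance. An unstratified log-rank test does not credit that balance. If PS is prognostic, its variance estimate is too large, it rejects below its nominal level, and it loses power. It also pools two risk groups whose mix in the risk set changes over time, which dilutes the contrast further.

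What is at stake is efficiency in the between-arm EFS test, and in the OS test if it is run. Power for such a test is low even at full accrual, so a loss that wording alone can avoid is worth removing.

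**Working it through.** **1. The plan's own figures.** The documents state power and alpha only for the per-arm rule (Sections 13.3 and 13.4.1): at least 36 of 62 alive at 18 months, p0 = 0.50, p1 = 0.63, with a stop if 11 or fewer of 30 have an R0 resection.

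- P(X ≥ 36 | 62, 0.63) = 0.826. P(pass interim | R0 60%) = 1 − 0.0083 = 0.9917. Product 0.819; stated 82%.
- Interim stopping: 0.431 at R0 40% and 0.0083 at R0 60%; stated 43% and 0.8%.
- P(X ≥ 36 | 62, 0.50) = 0.126. Times P(pass | R0 40%) = 0.569, this gives 0.072; stated 0.07. With R0 at 60% it is 0.125, which is a separate matter.

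The products take R0 and OS as independent. No between-arm test enters any of these figures, so stratifying leaves them unchanged.

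**2. Reference power for a between-arm log-rank.** The design contrast of 18 vs 27 months (Section 13.3) gives a hazard ratio of 18/27 = 0.667. With d events, power = Φ(√(d/4)·|ln HR| − 1.96). At d = 80: √20 × 0.4055 − 1.96 = −0.147, so power is about 44%.

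**3. Simulation of the two log-rank tests.**
- From the documents: 62 per arm; 34 months of accrual and 18 months of further follow-up; control median 18 months; treatment HR 0.667; PS 1 share 36%, guided by 64% PS 0 in the pilot (Section 1.4.4).
- Assumed: PS hazard ratio h from 1.0 to 3.0; exponential survival within stratum; exact balance within PS; two-sided 5%; 50% PS 1 as sensitivity.
- With q the PS 1 share, the baseline hazard λ solves (1 − q)e^(−18λ) + q·e^(−18λh) = 0.5.
- Unstratified: Z = U/√V, with U = Σ(g − p) and V = Σp(1 − p) over events, where g is the arm indicator and p the arm's share of the risk set. Stratified: Z = (U₀ + U₁)/√(V₀ + V₁), computed within PS 0 and PS 1.

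Results, 40,000 trials per setting, unstratified / stratified, in %:

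| PS HR | Type I, 36% PS 1 | Power, 36% PS 1 | Gain (points) | Type I, 50% PS 1 | Power, 50% PS 1 | Gain (points) |
|---|---|---|---|---|---|---|
| 1.0 | 5.06 / 5.07 | 44.10 / 43.76 | −0.34 | 5.13 / 5.07 | 43.77 / 43.31 | −0.46 |
| 1.3 | 4.87 / 5.02 | 43.40 / 43.47 | 0.07 | 5.09 / 5.19 | 43.03 / 43.21 | 0.18 |
| 1.5 | 4.71 / 4.99 | 42.16 / 42.99 | 0.83 | 5.02 / 5.32 | 42.54 / 43.53 | 0.99 |
| 2.0 | 4.20 / 5.08 | 39.88 / 43.19 | 3.31 | 4.37 / 5.30 | 39.50 / 43.04 | 3.54 |
| 3.0 | 3.34 / 5.15 | 33.26 / 42.30 | 9.04 | 3.21 / 5.22 | 33.51 / 42.76 | 9.25 |

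The Monte Carlo standard error at a 5% level is √(0.05 × 0.95/40,000) = 0.11 points. With 50% PS 1, conservatism is not visible until h = 2.0, and the stratified test sits slightly above 5%.

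**4. Small, unequal arms.** A second simulation took 62 vs 30 patients (the 30 is assumed), treatment HR 0.6, average median 22 months, censoring uniform over 18 to 52 months, 50% PS 1 and 6,000 trials per cell. At PS HR 1.5 / 2.0 / 2.5, power was 35.4 / 34.1 / 32.4% unstratified and 36.3 / 37.9 / 38.1% stratified. Null rejection was 4.8 / 4.7 / 4.1% against 4.9 / 5.1 / 5.7%. The standard error is √(0.05 × 0.95/6,000) = 0.28 points, so 5.7% lies 0.7/0.28 = 2.5 standard errors above nominal.

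**5. Chi-square on 18-month OS.** In the step 3 setting with 36% PS 1 and PS HR 1.0 / 1.5 / 2.0 / 3.0, chi-square type I error is 5.9 / 5.6 / 5.3 / 4.2%. Power is 32.7 / 31.7 / 30.4 / 27.0% for chi-square and 32.7 / 31.8 / 30.6 / 29.2% for Cochran-Mantel-Haenszel. Nothing was computed for R0, pCR or adverse events.

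**The case against.** The strongest case against is that nothing in the trial turns on these tests. The powered analysis is a single-arm count in each arm, and Section 13.4.1.3 picks the winner on the higher observed 18-month OS rate, however small the margin, so no p-value decides it. A mildly conservative secondary test is not a validity error. The PS effect is assumed, and at a hazard ratio of 1.3 the gain is within simulation noise. All of this stands and limits the point to a modest efficiency gain.

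The closure of Arm 2 also cuts against it. Section 13.4.1.2 ties a positive finding to full accrual. If Arm 2 stopped short of 62, the OS log-rank is not triggered as written. Arm 1 patients enrolled after closure were not randomized against Arm 2, and PS strata do not repair that. This stands too, and it is why the fix restricts the comparison to concurrently randomized patients.

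Section 2.3 already brings the stratification factor into the primary result. That is true, but it does not reach EFS.

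What remains is that the EFS log-rank is unconditional and still in the current text. PS is the one factor chosen for stratification, and Section 13.4.2.4 also uses performance status in its imputation models, so the plan itself treats PS as informative.

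**Conclusion.** The point holds for the log-rank tests, at modest size. With 62 per arm and treatment HR 0.667, an assumed PS hazard ratio of 1.3 to 2.0 costs about 0 to 3.5 power points; a loss near 9 points needs a value near 3. If PS has no effect, stratifying costs about 0.3 points at 36% PS 1. The figures come from an OS model. The documents give no EFS distribution, so they are only indicative for EFS.

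A reader might infer more than the documents support:

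- **That every between-arm test is conservative.** The chi-square test on 18-month OS was not below 5% up to a PS hazard ratio of 2.0, and Cochran-Mantel-Haenszel gained only about 0.2 points there. The documents do not show that PS predicts R0, pCR or adverse events.
- **That the design figures or the choice of arm are compromised.** The 82% power, the 0.07 alpha and the per-arm rules involve no between-arm test.
- **That the reported treatment hazard ratio would be biased toward 1.** Section 13.4 lists no between-arm hazard ratio. Its Cox models relate pCR or R0 status to outcome.
- **That closing Arm 2 makes the missing strata the main problem.** Non-concurrent Arm 1 patients matter more for these comparisons.

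**What to change.** In Section 13.4.2.1, and in 13.4.1.3 for the OS comparison if it is triggered, specify the log-rank test stratified by ECOG PS (0 vs 1) among patients randomized while both arms were open. Keep the unstratified log-rank as a sensitivity analysis.

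Keep chi-square with the Fisher fallback for 18-month OS, R0, pCR and adverse events. A Cochran-Mantel-Haenszel version is optional as a sensitivity analysis where tables are not sparse; pCR may well be sparse (2 of 15 specimens in the pilot, Section 1.4.4). Leave the per-arm decision rules as they are.

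The cost is wording only, because PS is recorded at randomization for every patient in the comparison. The downside is that the stratified test may be slightly liberal in small, unequal arms (0.057 under the null in the 62 vs 30 simulation, at a PS hazard ratio of 2.5). Reporting the unstratified result beside it lets a reader see whether that matters.
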